APPENDIX 3. ANALYSIS VISIT WINDOWS

Analysis Visit	Nominal Visit	Target Visit Day (Study Day)	Fasting Lipids, Glucose and HbA1c (Study Day)	Safety Lab, Vital Signs and Physical Exams (Study Day)	hs-CRP (Study Day)
Baseline	T1	1	Day 1/before 1 st dose		
Month 1	T2	30	-	2 – 60	-
Month 3	T3	91	2 – 136	61 – 136	-
Month 6	T4	182	137 – 273		2 – 273
Month 12	T6	365	274 – 456		
Month 18	T8	547	457 – 638		
Month 24	T10	730	639 – 821		
Month 30	T12	912	822 – 1003		
Month 36	T14	1095	1004 – 1186		
Month 42	T16	1277	1187 – 1368		
Month 48	T18	1460	1369 – 1551		
Month 54	T20	1642	1552 – 1733		
Month 60	T22	1825	1734 – 1916		
Month 66	T24	2007	1917 – 2098		

APPENDIX 4. IMPUTATION OF DATES

The following rules will be used to impute partial missing dates. Note that imputed dates may be used to calculate ‘study day’ but will NOT be presented in the listings.

AE start date	If only Day is missing:	If the AE start year and month are the same as that for the first dose (Day 1) date, then the AE start day will be imputed as the day of first dose date; otherwise, the AE start day will be imputed as the first day of the month.
	If both Day and Month are missing:	If AE start year is the same first dose year, then the AE start Month and Day will be imputed as the Month and Day of first dose date; otherwise, the AE start date will be imputed as 01 January.
	If Year of AE start date is missing or AE start date is complete missing:	The AE start date will be imputed as the first dose date.
AE stop date	If only Day is missing:	If only Day is missing and AE stop month and year are the same as the month and year of the EOS date, use the EOS date; otherwise the last day of the month will be imputed.
	If both Day and Month are missing:	If both Day and Month are missing and AE stop year is the same as the year of the EOS date, the EOS date will be used to impute. If the year of the AE end date precedes the year of the EOS date, AE end month and day will be set to 31 December.
	If the Year of AE stop date is missing or AE stop date is completely missing:	If the AE stop date is completely missing, 1) if the “Ongoing” status is “Yes”, the EOS Date will be assigned to the stop date; 2) if the “Ongoing” status is “No” or missing, the stop date will be assigned as the Date of Informed Consent, or the start date if present (partially imputed if necessary) and later. If only Year is missing, the EOS year will be assigned to the stop date.

AE = adverse event; EOS = End-of-Study

Medication start date	If only Day is missing:	If only Day is missing, the first day of the month will be assumed.
	If only Day and Month are missing:	If both Day and Month are missing, the first day of the year will be assumed.
	If only Year is missing or date is completely missing:	If medication start date is completely missing, the informed consent signature date or medication end date whichever is earlier, will be used to impute.

AE start date	If only Day is missing:	If the AE start year and month are the same as that for the first dose (Day 1) date, then the AE start day will be imputed as the day of first dose date; otherwise, the AE start day will be imputed as the first day of the month.
	If both Day and Month are missing:	If AE start year is the same first dose year, then the AE start Month and Day will be imputed as the Month and Day of first dose date; otherwise, the AE start date will be imputed as 01 January.
	If Year of AE start date is missing or AE start date is complete missing:	The AE start date will be imputed as the first dose date.
		If only Year is missing, then informed consent signature year will be used to impute.
Medication stop date	If only Day is missing	If only Day is missing, the last day of the month will be assumed.
	If both Day and Month are missing	If both Day and Month are missing, the medication stop month and day will be set to 31 December.
	If Only Year is missing or medication end date is completely missing	If medication end date is completely missing, 1) if the “Ongoing” status is “Yes”, the EOS Date will be assigned to the stop date; 2) if the “Ongoing” status is “No” or missing, the end date will be assigned as the Date of Informed Consent, or the start date if present (partially imputed if necessary) and later. If only Year is missing, the EOS year will be assigned.
Other dates	If only Day is missing	If only Day is missing, the last day of the month will be assumed.
	If only Day and Month are missing:	If both Day and Month are missing, the first day of the year will be assumed.
	If the year is missing, or the date is completely missing.	Will not be imputed.

AE = adverse event; EOS = End-of-Study

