7.4.2. Antidiabetic Medications

For this study, antidiabetic medications are defined based on approved medications that lower blood glucose (Appendix 8).

Baseline antidiabetic medications are defined for the FAS as those ongoing at the time of randomization.

Patients are considered to have had a *change in background antidiabetic medications* if they had any new antidiabetic medications that either started, stopped or had a dose change during the 12 weeks (84 days) prior to screening (Visit S1) to within 12 months (365 days) post randomization. These patients are excluded from a sensitivity analysis of Month 12 HbA_{1c} response.

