8.5.1. Imputation of Missing Dates

For adverse events, and for prior and concomitant medications, if the start or end dates are incomplete, the date will appear as-is (partial or missing) in the listings. When full date is needed, e.g., to compute the Study Day, imputation rules specified in Appendix 4 will be used unless otherwise specified. In essence, AEs of uncertain start date will be considered as having started after the first dose. Medications of uncertain start or end dates will be considered as having started before, or continued after the first dose, respectively.

For LMTs (Section 7.6) and antidiabetic medications (Section 7.4.2), it is important to determine whether they were being used at baseline (i.e., the time of randomization, Section 7.6.3).

- When the medication start date is partially missing, it is imputed using the default rule. If the impute start date is before the date of randomization, and the end date is either completely missing with ongoing status of no, or only contains a year that is the same as the date of randomization, the end date is imputed with the later of the medication start date and the date of informed consent. Otherwise the default rule is used to impute the end date.

- When the medication start date is completely missing, and if the end date is either completely missing with ongoing status of no, or only contains a year that is the same as the date of randomization, both start and end dates are imputed with the date of informed consent.
- Otherwise, the start/end dates are inputted using the default rule.

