13.2. Antidiabetic Medications

For patients with diabetes at baseline in the FAS, and the subset with inadequately control diabetes, baseline antidiabetic medications (see [Section 7.4.2](#)) will be summarized by preferred names and treatment group.

Patients who had a change to antidiabetic medications will be summarized by baseline glycemc status:

- within 12 weeks before screening through 12 months (365 days) post-randomization;
- within 12 weeks before screening to before randomization (only applicable for patients with diabetes at baseline);
- from randomization through 12 months (365 days) post-randomization.

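### An antidiabetic drug in use at randomization with no start date on record is given the consent date as its start, so a stable user appears to be coded as having changed medication and dropped from the Month 12 HbA1c sensitivity analysis

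*SAP*

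**What the plan says.** SAP 7.4.2 defines a change in background antidiabetic medication through "any new antidiabetic medications that either started, stopped or had a dose change during the 12 weeks (84 days) prior to screening (Visit S1", with the window running on to 365 days after randomization. Patients who meet the definition are left out of a sensitivity analysis of Month 12 HbA1c.

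SAP 13.2 tabulates patients with a change over three periods. Two reach back before screening: one runs from 12 weeks before screening to 12 months after randomization, and the other is "within 12 weeks before screening to before randomization (only applicable for patients with diabetes at baseline"). The third starts at randomization.

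SAP 8.5.1 has special date rules for lipid-modifying and antidiabetic drugs because "it is important to determine whether they were being used at baseline". The rule for an absent start date opens: "When the medication start date is completely missing, and if the end date is either completely missing with ongoing status of no". It also covers an end date that gives only the year of randomization, and in both situations it sets start and end to the consent date. For everything else, "Otherwise, the start/end dates are inputted using the default rule".

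That default is in SAP Appendix 4. For the start: "If medication start date is completely missing, the informed consent signature date or medication end date whichever is earlier, will be used to impute". For the stop of a drug with no end date: "if the “Ongoing” status is “Yes”, the EOS Date will be assigned to the stop date".

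**The concern.** A consent-date start answers the question that 8.5.1 set out to answer: the drug counts as in use at randomization. The same imputed date then appears to feed a second question, whether background therapy changed recently. There it gives the wrong answer for a long-term user. Having no information about the start becomes a positive finding of a recent start.

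The sensitivity analysis is meant to show the HbA1c effect in patients on stable background therapy. If it loses some of those patients because of a date convention, a difference from the main analysis could be put down to medication change when part of it comes from the selection. The two 13.2 rows that include the 12 weeks before screening would also count changes that did not happen.

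**Working it through.** The plan gives no figure to reproduce, so the check follows the rules through.

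**Inputs**
- Change window: S1 minus 84 days to randomization plus 365 days (SAP 7.4.2).
- Consent: obtained before the Visit S1 procedures (Protocol 10.6.1).
- Randomization: about 35 days after S1; screening may be extended by 5 weeks (Protocol 6.1 and 10.6.1).
- Date rules: SAP 8.5.1 and Appendix 4.

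**Rule chain for an ongoing drug with no start date**
1. The special rule in 8.5.1 does not apply, because the drug is ongoing.
2. Under the Appendix 4 default, the stop date becomes the end-of-study date.
3. The start is the earlier of consent and stop, which is consent.
4. Consent lies at or just before S1, inside the window. It would fall outside only if it preceded S1 by more than 84 days.

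**Example** (dates assumed): consent = S1 = 1 June 2018; randomization = 6 July 2018; end of study = 1 August 2022. The window is 9 March 2018 to 6 July 2019. Its span is 84 + 35 + 365 = 484 days, or 84 + 70 + 365 = 519 days with extended screening.

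| Record | Imputed start | In use at randomization | Start in window |
|---|---|---|---|
| No start date, ongoing | 1 Jun 2018 | Yes | Yes |
| No start date, stop recorded 1 Dec 2020 | 1 Jun 2018 | Yes | Yes |
| Start year 2010 only, ongoing | 1 Jan 2010 | Yes | No |
| No start date, stop recorded 10 Jan 2018 | 10 Jan 2018 | No | No |

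The first two rows are the problem. In the third, partial information is enough to keep the patient. In the fourth, the patient is not a current user. A start lacking only the year takes the consent year, so its result depends on the calendar date: 15 April is flagged and 15 January is not.

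Within 13.2, a consent-date start falls in both periods that begin 12 weeks before screening. It does not fall in the period that begins at randomization.

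**Size.** The documents give no rate of missing start dates, so the following are assumptions. If a share m of the stable patients is wrongly dropped, the confidence interval widens by the factor 1/√(1−m):

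| m | Widening |
|---|---|
| 1% | 0.5% |
| 5% | 2.6% |
| 10% | 5.4% |
| 20% | 11.8% |

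To go from drugs to patients, let p be the share of records with no start date and k the number of drugs per patient. If records are independent, m = 1−(1−p)^k. With k = 2, that is 9.8% for p = 5% and 19.0% for p = 10%. If missing dates cluster completely within patients, m falls to p, that is 5% or 10%.

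**The case against.** - **Section 15.4.4.** The SAP contents list this section, on additional diabetes analyses, and it is the natural home for the analysis in question. Its text is not in the copy available, so it may contain an override. This stands and makes the conclusion conditional.
- **The word new in 7.4.2.** It could be read as sparing a drug taken for years. But the SAP does not define it, it sits awkwardly beside stopping and dose change, and a programmer has only the recorded or imputed start by which to judge newness. It does not clearly protect these patients.
- **Use of imputed dates for the flag.** The SAP does not say in so many words that imputed dates feed the 7.4.2 flag. Section 8.5.1 applies imputation when a full date is needed, with Study Day as its example. Using it for the flag is the natural reading, and no text that we have exempts it, but it remains an inference.
- **Frequency.** Protocol 8.2 requires start and stop dates for concomitant medication, so the condition may be rare. That limits the size. Even so, the SAP wrote rules for completely missing starts.
- **Conservatism.** Excluding patients whose stability is undocumented can be defended. The plan does not give that reason, and the result would still be reported as a medication change.

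A reader might infer that every uncertain start date triggers the problem. The documents do not support this: a known earlier year is imputed to 1 January, and a known month and year to the first of that month.

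**Conclusion.** The point holds in a limited form. Under SAP 8.5.1 and Appendix 4, a completely missing start on an antidiabetic drug in use at randomization becomes the consent date, which lies inside the 7.4.2 window. Unless 15.4.4 or the word new overrides this, a stable user is coded as changed, dropped from one sensitivity analysis, and counted in two descriptive rows of 13.2.

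The reach is small. The main Month 12 HbA1c analysis (SAP 15.3.4) does not use the flag. The endpoint lies outside the testing hierarchy, with nominal p-values (SAP 8.3, Protocol 15.7).

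Two stronger conclusions might be drawn and should not be:
- **A material share of patients is lost.** The documents give no rate. Figures such as 10% or 19% need assumed missingness and independence between one patient's drugs. They also count patients whose genuine change would have excluded them anyway.
- **The treatment comparison is biased.** Missing start dates for drugs begun before randomization should be similar in the two arms. The expected harm is a wrongly selected subset, two overstated rows and some lost precision.

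**What to change.** Add one sentence to SAP 7.4.2, with a cross-reference in 13.2. For the change flag and the 13.2 rows only, a completely missing start on an antidiabetic drug that was in use at consent and ongoing at randomization is treated as falling before the 84-day window. Use at consent can be taken from the medication review at Visit S1 (Protocol 10.6.1).

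Leave the Appendix 4 imputation in place for partly reported start, stop and dose-change dates. Ignoring every imputed date would go too far: a drug started in a known month after randomization, with only the day missing, is a genuine change and must still count. Report the number of patients affected by the new sentence, by arm, and check it against Section 15.4.4.

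The cost is a sentence and a small program change. The downside is that a truly recent start with no date information would be counted as stable; the count by arm shows how far that could matter.

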7.6.4. Cross-in LMT

For patients in the FAS, cross-in LMT is defined as either initiation of new non-statin LMT or an increase in statin intensity after randomization that meets at least one of the following criteria:

1. Any statin, regardless of the specific drug, started after randomization, with increased intensity if used at baseline, and continued for 90 days or more.
2. Non-statin oral prescription LMTs (Bile Acid Sequestrants, Fibrates, Niacin Derivatives, Ezetimibe, commercial Bempedoic Acid, commercial Bempedoic Acid and Ezetimibe FDCCP, as defined in Section 7.6.1) that were not used at baseline (same preferred name), started after randomization and continued for 90 days or more.
3. PCSK9i started after randomization, not used at baseline (for evolocumab), or with increased intensity if used at baseline (specifically, for alirocumab switching from 75 mg once every two weeks to 150 mg once every two weeks or 300 mg once every 4 weeks), and continued for 90 days or more if mAb (evolocumab or alirocumab); or ≥ 1 dose for siRNA (inclisiran) after randomization, and before the EOS visit.

Since change of dosing regimen will result in a new entry on the medication CRFs, to determine the treatment duration, entries for medications of the same class (any statin, either of the PCSK9i mAbs), or the same preferred name (non-statin oral LMT) will be combined if the gaps between entries are ≤ 7 days (for oral drugs), or ≤ 30 days (for PCSK9 mAb injections).

The date of starting first adjunctive cross-in LMT is defined to be the start date of the first medication that meets the cross-in criteria.

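### A statin, oral lipid drug or PCSK9 antibody started after randomization, with no end date and not marked ongoing, is given a duration of 0 days and cannot count as cross-in on that record alone

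*SAP*

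**What the plan says.** Three parts of the SAP act together.

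- **Appendix 4, medication stop date.** If the end date is completely missing, the Ongoing field decides. For Yes: "if the “Ongoing” status is “Yes”, the EOS Date will be assigned to the stop date". For the other case, "if the “Ongoing” status is “No” or missing", the rule is "the end date will be assigned as the Date of Informed Consent, or the start date if present (partially imputed if necessary) and later".
- **Section 8.5.1, special rules for lipid-modifying and antidiabetic drugs.** One rule covers a partly missing start date, under the condition "If the impute start date is before the date of randomization"; beyond that, "Otherwise the default rule is used to impute the end date". A second covers a completely missing start date. Everything else goes to Appendix 4: "Otherwise, the start/end dates are inputted using the default rule".
- **Section 7.6.4, definition of cross-in.** An oral non-statin lipid drug not used at baseline counts if it "started after randomization and continued for 90 days or more". Statins and PCSK9 antibodies face the same 90-day minimum. Inclisiran needs only one dose. Entries are merged before duration is computed if the gap is at most 7 days (oral drugs) or 30 days (PCSK9 antibodies).

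The cross-in date is used in Section 13.3 (counts and time to first cross-in, FAS). It is also used in Section 15.4.3, in the PPS: MACE-4 and MACE-3 are censored 30 days after the first cross-in drug starts, and the Month 6 LDL-C and hs-CRP summaries drop values taken more than 7 days after that start.

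**The concern.** Section 8.5.1 says that its special rules are there to settle whether a drug was in use at baseline. No rule addresses how long a drug lasted if it started after randomization, although the cross-in definition depends on that duration. Such records take the general default, which ends them on the day they began. The 90-day test is then decided by the imputation and not by anything the site reported.

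At stake is the analysis meant to show the treatment effect without added lipid therapy. A patient whose only added drug has such a record is not censored at cross-in, so follow-up on that drug stays in the pre-cross-in hazard ratios. The patient is also missing from the cross-in counts.

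**Working it through.** The plan gives no figure on this point to reproduce. The check is date arithmetic on its rules.

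**Step 1: which rule applies.** Take a lipid drug with a complete start date after randomization, no end date, and Ongoing No or missing. The first 8.5.1 rule needs a partly missing start date imputed before randomization; the second needs a completely missing start date. Neither fits, so Appendix 4 applies. A partly missing start date imputed after randomization ends in the same place.

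**Step 2: imputed end date.** End = later of (consent date, start date). Consent precedes randomization, which precedes the start. So end = start, and end − start = 0 days (1 day if both ends are counted).

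**Step 3: the 90-day test.** Assumed dates for illustration: consent 1 January 2018, randomization 5 February 2018, EOS 15 June 2022, which is 1591 days from randomization to EOS.

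| Start (days after randomization) | Ongoing Yes: EOS − start | Ongoing No or missing | 90 days met? |
|---|---|---|---|
| 1 | 1591 − 1 = 1590 | 0 | Yes / No |
| 30 | 1591 − 30 = 1561 | 0 | Yes / No |
| 200 | 1591 − 200 = 1391 | 0 | Yes / No |
| 800 | 1591 − 800 = 791 | 0 | Yes / No |

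The last column gives the result for Ongoing Yes, then for No or missing. For a start at day 200, the true duration could lie anywhere from 0 to 1391 days; the rule always takes 0.

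**Step 4: exceptions.**

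- *Inclisiran.* One dose suffices, so the end date does not matter.
- *Merged entries.* The gap is measured from the undated entry's imputed end, which is its start. A second oral entry that starts 5 days later and lasts 85 days gives 5 + 85 = 90 days and qualifies. If it starts 8 days later, the gap exceeds 7 days: the entries stand alone at 0 and 85 days, and neither qualifies, although together they span 8 + 85 = 93 days. For PCSK9 antibodies the limit falls between 30 and 31 days.
- *Another qualifying record.* The patient is still flagged, but from that record's own start date.

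**Step 5: partial end dates.** Appendix 4 extends an end date with only the day missing to the month's end, and one with only a year to 31 December. Only a completely missing date collapses to the start.

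**The case against.** The strongest reply is that few records should be affected and little depends on them. Protocol Section 8.2 requires start and stop dates for concomitant drugs, medications are reviewed about every 3 months, and Protocol Section 19.3 tells sites not to leave fields blank. Section 8.5 imputes nothing for the primary analysis of the primary and key secondary endpoints, and that analysis does not censor at cross-in. All of this stands and limits the point. It does not remove it: Protocol Section 19.3 allows an item to be entered as not available, and Protocol Section 8.2 has the statin form collect stop dates only when they can be obtained.

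Three stronger readings are tempting, and the documents do not support them.

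- *Appendix 4 contradicts Section 8.5.1 here.* That section says "Medications of uncertain start or end dates will be considered as having started before, or continued after the first dose, respectively". The sentence places a drug before or after first dose. It does not speak to the duration of a drug started after randomization, so for these records there is a gap and not a contradiction.
- *The consent-date rule is also wrong for drugs started before randomization and should be reversed.* Section 8.5.1 itself uses the later of start and consent for lipid drugs with a partly missing pre-randomization start that are marked not ongoing. The statin form records any statin ever taken. Running undated records through randomization, or to EOS, could turn old failed statins into baseline statins. Section 7.6.3 takes the highest-intensity baseline statin and Section 7.6.4 requires an increase over baseline, so real cross-ins could then be hidden.
- *A patient count can be given.* Assuming 1,000 to 1,700 courses, of which 1% to 5% are affected, gives 1,000 × 0.01 = 10 to 1,700 × 0.05 = 85 courses. The documents support neither input. Courses are not patients, and a course that truly lasted under 90 days is correctly left out.

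**Conclusion.** The point holds in a limited form. For statins, oral non-statin lipid drugs and PCSK9 antibodies started after randomization, with a completely missing end date and Ongoing No or missing, the rule gives 0 days and the record alone fails the 90-day test. Any such course that really lasted 90 days or more, in a patient with no merged or other qualifying entry, is misclassified.

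The effect is confined to the Section 13.3 cross-in summaries and, in Section 15.4.3, to the pre-cross-in MACE-4 and MACE-3 analyses and the Month 6 LDL-C and hs-CRP summaries. Its size cannot be computed, because the documents give no count of such records. A reader might infer that the trial's main result is at risk; it is not, since the primary and key secondary FAS analyses do not use the cross-in date.

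A reader might also infer an imbalance between arms. The LDL-C trigger of 25% or more above baseline makes cross-in plausibly commoner on placebo, but no figure in the documents shows it. On that assumption, missed cross-ins would leave the Section 15.4.3 hazard ratios closer to those without cross-in censoring.

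**What to change.** Add a rule to Appendix 4 or Section 8.5.1, limited to lipid drugs started after randomization with a completely missing end date:

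1. Do not set the end date to the start date.
2. If Ongoing is missing, treat the drug as ongoing, with the EOS date as its end.
3. If Ongoing is No, count the course as cross-in in Section 15.4.3, provided that it meets the other criteria of Section 7.6.4, and repeat the analysis with it not counted. The start date is available, so the censoring date is defined.
4. Report a blinded count of the affected records before unblinding, and list them by arm afterwards.

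For drugs started before randomization, keep the consent-date rule. Reconcile the wording there: the Section 8.5.1 sentence on uncertain dates does not match what Appendix 4 does to a drug started before consent, and the lipid-drug rules in 8.5.1 apply when Ongoing is No, whereas Appendix 4 applies when it is No or missing.

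The cost is a few sentences, a re-run of the medication derivation and one repeated sensitivity analysis. The downside is that a few courses that truly lasted under 90 days will be counted as cross-in; for records marked No, the repeat analysis shows whether that matters.
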